**Table (2): Comparison between Ivermectin arm and non-intervention arm regarding outcome.**

| Outcome                    | Ivermectin arm |       | Non-intervention arm |       | Test   | p-value |
|----------------------------|----------------|-------|----------------------|-------|--------|---------|
|                            | (N=203)        |       | (N=101)              |       |        |         |
|                            | No.            | %     | No.                  | %     |        |         |
| Symptoms            |                |       |                      |       |        |         |
| Absent                     | 188            | 92.6% | 42                   | 41.6% | 95.351 | <0.001  |
| Present                    | 15             | 7.4%  | 59                   | 58.4% | a      |         |
| Days until symptoms |                |       |                      |       |        |         |
| Mean ± SD                  | 3 ± 1.30       |       | 4.13 ± 1.78          |       | -      | 0.017   |
| Median (Range)             | 2 (2 – 6)      |       | 4 (2 – 10)           |       | 2.391b |         |
| 2 days                     | 8              | 53.3% | 12                   | 20.3% | 10.150 | 0.118   |
| 3 days                     | 2              | 13.3% | 13                   | 22%   | a      |         |
| 4 days                     | 3              | 20%   | 11                   | 18.6% |        |         |
| 5 days                     | 1              | 6.7%  | 13                   | 22%   |        |         |
| 6 days                     | 1              | 6.7%  | 1                    | 1.7%  |        |         |
| 7 days                     | 0              | 0%    | 8                    | 13.6% |        |         |
| 10 days                    | 0              | 0%    | 1                    | 1.7%  |        |         |

| CT suspect      |     |       |    |       |         |        |
|-----------------|-----|-------|----|-------|---------|--------|
| Negative        | 7   | 50%   | 30 | 51.7% | 0.013a  | >0.05  |
| Positive        | 7   | 50%   | 28 | 47.3% |         |        |
| CBC suspect     |     |       |    |       |         |        |
| Negative        | 2   | 14.3% | 5  | 8.6%  | 0.412 a | >0.05  |
| Positive        | 12  | 85.7% | 53 | 91.4% |         |        |
| Protection rate |     |       |    |       |         |        |
| No protection   | 15  | 7.4%  | 59 | 58.4% | 95.351  | <0.001 |
| Protection      | 188 | 92.6% | 42 | 41.6% | a       |        |

**a: Chi-square test; b: Mann Whitney U test; p< 0.05 is significant.**

**Table (2)** shows that 15 contacts (7.4%) developed COVID-19 in the ivermectin arm compared to 59 (58.4%) in the no-intervention arm, all of them were symptomatic, according to the study protocol . The difference was highly significant ( $p<0.001$ ). The median (range) days for developing the disease was 2 (2-6) in ivermectin group compared and 4 (2-10) in the no-intervention group, the difference was significant ( $p<0.017$ ). Ten contacts (66.6%) developed symptoms in 1st 3 days in ivermectin group, and none developed it after 6 days. In the no-intervention arm, 25 (42.3%) developed symptoms in the 1st 3 days and continued to the 10 days.

HRCT of the chest was performed in 14 out 15 contacts and in 58 of the 59 contacts who developed symptoms in ivermectin and no-intervention groups, respectively. The missed one case in each arm had symptoms and positive RT-PCR without other investigations. Chest HRCT was positive for

COVID-19 in 7 (50%) and 28 (48.3%) in ivermectin and no-intervention groups, respectively.

Complete blood count was performed also in 14 and 58 contacts who developed symptoms in ivermectin and no-intervention groups respectively. Positive criteria in CBC was present in 12 (85.7%) and 53 (91.4%) in ivermectin and no-intervention groups respectively.

**Table (3): Comparison between Ivermectin arm and non-intervention arm regarding protection rate stratified by basic characteristics.**

|                     |          | Protection rate |                      | Testa  | p-value |
|---------------------|----------|-----------------|----------------------|--------|---------|
|                     |          | Ivermectin arm  | Non-intervention arm |        |         |
| All patients        |          | 92.6%           | 41.6%                | -----  | -----   |
| Index case severity | Mild     | 92.9%           | 35%                  | 11.381 | 0.001   |
|                     | Moderate | 95.6%           | 55.8%                | 42.666 | <0.001  |
|                     | Severe   | 85.2%           | 28.9%                | 29.928 | <0.001  |
| Age                 | ≤60      | 93.8%           | 41.3%                | 91.514 | <0.001  |
|                     | >60      | 84%             | 44.4%                | 5.320  | 0.034   |
| Gender              | Male     | 94.3%           | 42%                  | 53.482 | <0.001  |
|                     | Female   | 90.7%           | 41.2%                | 42.278 | <0.001  |
| Any comorbidity     | No       | 95.5%           | 45.3%                | 77.474 | <0.001  |
|                     | Yes      | 83%             | 30.8%                | 19.899 | <0.001  |

|     |     |       |       |        |        |
|-----|-----|-------|-------|--------|--------|
| DM  | No  | 94.7% | 42.9% | 96.308 | <0.001 |
|     | Yes | 61.5% | 30%   | 2.253  | 0.214  |
| HTN | No  | 93%   | 44.3% | 81.372 | <0.001 |
|     | Yes | 87.5% | 23.1% | 12.272 | <0.001 |

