### **Research question**

Is oral Ivermectin can prevent symptomatic COVI-19 infection in family close contacts with patients diagnosed as having the disease by RT-PCR

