### **Aim**

To study oral Ivermectin as a prophylactic treatment in family close contacts with COVID-19 patients in the form of development of symptoms

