### **Follow up:**

1-These asymptomatic persons will be followed up for 2 weeks after the diagnosis of index case for:

Symptoms development,

Radiological evaluation if symptoms developed (HRCT chest)

Swabs for SARS-2 Virus if symptomatic

Recording possible side effects during treatment: eg sleepiness and fatigue

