## Consort Flow diagram of Ivermectin prophylaxis trial

## **Statistical analysis**

All data were collected, tabulated and statistically analyzed using SPSS 22.0 for windows (IBM Inc., Chicago, IL, USA) and MedCalc 13 for windows (MedCalc Software Bvba, Ostend, Belgium). Continuous Quantitative variables were expressed as the mean  $\pm$  SD & median (range), and categorical qualitative variables were expressed as absolute frequencies (number) & relative frequencies (percentage). Continuous data were checked for normality by using Shapiro Walk test. Mann-Whitney U test was used to compare between two groups of non-normally distributed data. Categorical data were compared using Chi-square test or Fisher's exact test when appropriate. Relative risk and its 95%Confidence interval (CI) was calculated to estimate risk of COVID-19 infection in addition forest plot was plotted. Univariate and multivariate binary logistic regression were built to find predictors for COVID-19 protection. All tests were two sided. p-value < 0.05 was considered statistically significant.

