## Results

As regard index cases, there were 9 (11.8%) mild , 44 (57.9%) moderate and 23 (30.3%) severe cases. In the ivermectin group, there were 8 (53.3%) mild , 6 (40%) moderate and 1 (6.7%) severe cases. While in the no-intervention group, there were 31 (52.5) mild, 21 (35.6%) moderate and 7 (11.9%) cases.

[figure not shown]

Figure (1): Scatter plot shows relationship between contact time in days and number of contacts that developed COVID-19; dashed line represent best fitted line (quadratic model).

There was insignificant linear correlation between contact time in days and number of contact that developed COVID-19. The appropriate forecasting for number of contact that developed COVID-19 based upon contact time in days was quadratic model.

[figure not shown]

Figure (2): Box plot shows relationship between isolation and number of contacts that developed COVID-19.

There was insignificant difference between index cases isolated at hospital and index cases isolated at home regarding number of contact that developed COVID-19 where mean number of contact that developed COVID-19 ( $\pm$ SD) was 2.14 ( $\pm$ 1.35) versus 2.07 ( $\pm$  2.26) respectively (p-value=0.280)

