**a: Chi-square test; p< 0.05 is significant.**

**Table (3)** shows that 7.4% contacts developed diseases in ivermectin group while they were 58.4% in no-intervention group. Contacts tend to be infected when the index case was severe; 14.8% and 71.1% in both groups, respectively. The protection rate for ivermectin was more prominent in contacts less than 60 years old (6.2% infected compared to 58.7% if no intervention) , but still effective in elder than 60 years (16% infected compared to 55.6% if no intervention).

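### The Results describe a symptom outcome as infection, and print an RT-PCR result for only 2 of the 74 symptomatic contacts although swabs were planned for them

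*Combined protocol and SAP*

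**What the plan says.** The Aim sets the outcome "in the form of development of symptoms". The Research question is slightly narrower: "Is oral Ivermectin can prevent symptomatic COVI-19 infection in family close contacts". The Follow up section plans two weeks of observation, with HRCT if symptoms appear and "Swabs for SARS-2 Virus if symptomatic". It plans no test for contacts who remain well.

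Table (2) has a row for symptoms and a row for protection, with the same counts and the same chi-square. The text below it turns these counts into disease: 15 contacts "developed COVID-19 in the ivermectin arm compared to 59 (58.4%) in the no-intervention arm, all of them were symptomatic, according to the study protocol". On virology, the only statement about contacts is "The missed one case in each arm had symptoms and positive RT-PCR without other investigations". HRCT and complete blood count results are given for the remaining 14 and 58 symptomatic contacts.

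Elsewhere the label widens. The Statistical analysis section says that the relative risk "was calculated to estimate risk of COVID-19 infection". The text under Table (3) says "Contacts tend to be infected when the index case was severe" and gives percentages infected. The paragraph after Table (4) concludes that ivermectin protects against SARS-CoV-2 infection.

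**The concern.** Preventing symptoms, preventing confirmed symptomatic COVID-19 and preventing infection are three different claims. The trial counted the first. It planned to collect what the second needs, by swabbing symptomatic contacts, but the results are almost entirely absent from the printed report. It did not plan to measure the third, because a contact infected without symptoms would never be swabbed.

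At stake are the wording of the conclusion and the absolute effect for confirmed disease, which cannot be read from the printed results. No case definition is stated that says how symptoms, swab, HRCT and blood count combine to make a case.

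**Working it through.** **Inputs.** Table (2): symptoms in 15 of 203 (ivermectin) and 59 of 101 (no intervention); no symptoms in 188 and 42. Text under Table (2): HRCT positive in 7 of 14 and 28 of 58; blood count positive in 12 of 14 and 53 of 58; one RT-PCR-positive contact per arm, with neither of those tests. Results, opening paragraph: 9 + 44 + 23 = 76 index cases, and severity of the symptomatic contacts.

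**1. The plan's own figure.** Pearson chi-square without correction:

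304 × (15×42 − 188×59)² / (203 × 101 × 74 × 230) = 95.351.

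This matches both the symptom row and the protection row of Table (2). Protection therefore means absence of symptoms.

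**2. The symptom effect.**
- Risks: 15/203 = 7.4% and 59/101 = 58.4%; difference 51.0 points (Wald 95% CI 40.8 to 61.3).
- Relative risk 0.0739/0.5842 = 0.126. SE of the log = √(1/15 − 1/203 + 1/59 − 1/101) = 0.262; 95% CI 0.076 to 0.212.

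**3. Where the infected percentages come from.** Each one under Table (3) is 100 minus a protection rate in that table:

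| Subgroup | Ivermectin | No intervention |
|---|---|---|
| Severe index case | 100 − 85.2 = 14.8 | 100 − 28.9 = 71.1 |
| Age up to 60 | 100 − 93.8 = 6.2 | 100 − 41.3 = 58.7 |
| Age over 60 | 100 − 84 = 16 | 100 − 44.4 = 55.6 |

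These are symptom rates under another name.

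**4. What was not planned to be measured.** Symptom-free contacts: 188 + 42 = 230 of 304, with no swab planned.

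**5. Confirmation among the 74.**
- RT-PCR printed: 1 + 1 = 2 (2.7%). Not printed: 14 + 58 = 72 (97.3%).
- Support in those 72: HRCT positive in 7 + 28 = 35; blood count positive in 12 + 53 = 65, by criteria that are not defined.

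**6. Nearest comparison from printed data: HRCT positive or RT-PCR positive.**
- Ivermectin 7 + 1 = 8 of 203 (3.9%); no intervention 28 + 1 = 29 of 101 (28.7%).
- Relative risk 0.137. SE of the log = √(1/8 − 1/203 + 1/29 − 1/101) = 0.380; 95% CI 0.07 to 0.29. Risk difference 28.7 − 3.9 = 24.8 points.
- Events outside this definition: 15 − 8 = 7 and 59 − 29 = 30, together 37 of 74.
- A less favourable mix, all 15 ivermectin contacts against these 29, gives a relative risk of 0.26 (95% CI 0.14 to 0.46).

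**7. Arithmetic limits from the printed RT-PCR results alone.** The confirmed counts can lie anywhere from 1 to 15 and from 1 to 59. The extremes are 15/203 (7.4%) against 1/101 (1.0%), and 1/203 (0.5%) against 59/101 (58.4%). Neither is put forward as plausible. They show that the swab results are needed before confirmed disease can be quantified.

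**8. Clustering.** 304 / 76 = 4.0 contacts per index case on average. All intervals above treat contacts as independent and are likely to be too narrow. The documents give no within-household correlation with which to correct them.

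**The case against.** The strongest reply is that symptoms were the planned outcome, that the Research question and Hypothesis speak of symptomatic infection, and that the text under Table (2) says that all cases were symptomatic. On that view, infection is shorthand. This stands in part. Counting symptoms is not a fault, and the label in the Statistical analysis section is only a looser form of the planned target. It does not rescue the conclusion after Table (4), which drops the restriction to symptomatic disease, or the infected percentages under Table (3).

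A second reply is that the diagnosis had support. This also stands. Of the 72 contacts without a printed RT-PCR result, 65 had a positive blood count and 35 a positive HRCT, and the protocol itself treats a suggestive HRCT as grounds for exclusion. But the blood-count criteria are undefined. HRCT positivity may also partly reflect severity. The Results say "In the ivermectin group, there were 8 (53.3%) mild , 6 (40%) moderate and 1 (6.7%) severe cases", so moderate plus severe is 6 + 1 = 7; in the other arm it is 21 + 7 = 28. These totals equal the HRCT-positive counts of 7 and 28. Equal totals do not prove that the same people are involved, nor do they remove the diagnostic value of HRCT. They are a reason to treat the comparison in step 6 as an anchor and not as a replacement endpoint.

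A reader might go further and infer that swabs were not taken, or that 72 cases were unconfirmed or false. The documents do not support that. They show only that results are not printed; the flow diagram and figures are not available in the text, and the remark on the two contacts without other tests is compatible with RT-PCR having been done in others. Nor is it fair to say that the report presents all 304 contacts as tested, given its statements about symptomatic disease.

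**Conclusion.** The point holds as one of reporting and interpretation. The data describe development of symptoms. They do not support a conclusion about infection overall, and as printed they do not show how many of the 74 cases were confirmed virologically (2 shown, 72 not shown).

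The arm difference stays large under the nearest stricter definition that can be built from printed data: relative risk 0.14 against 0.126 for symptoms. The risk difference roughly halves, from 51 to about 25 points. That figure assumes that a positive HRCT or a printed positive RT-PCR is an acceptable stand-in for confirmation, and its interval ignores household clustering. A reader might infer that the effect vanishes once cases must be confirmed. The printed HRCT and RT-PCR counts do not suggest that, although RT-PCR alone cannot exclude it until the swab results are shown. What is unsupported is the infection label and the absolute effect for confirmed disease.

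**What to change.** 1. In the text under Table (3) and after Table (4), and for consistency in the Statistical analysis section, replace the infection wording with development of symptoms, or with RT-PCR-confirmed symptomatic COVID-19 where the swabs support it. This costs only editing.
2. Add to Table (2), by arm, the swabs done, positive, negative and missing for the 15 and 59 symptomatic contacts. Report confirmed symptomatic COVID-19 beside the symptom result, labelled post hoc if it was not predefined. This tabulates a test that the protocol planned, but the documents do not show that results exist for the other 72.
3. For missing swabs, give bounds that include differential confirmation: missing counted as cases in the ivermectin arm and as non-cases in the control arm, and the reverse. Applying the same rule to both arms would not bound this. Use intervals that allow for household clustering.

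The downside is that the event count and absolute effect may become smaller, and with many swabs missing the confirmed-case result may be imprecise.

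### Table 2's significant difference in days until symptoms (p=0.017) compares only the 15 and 59 contacts who fell ill, not the arms of 203 and 101

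*Combined protocol and SAP*

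**What the plan says.** Table (2) is titled "Comparison between Ivermectin arm and non-intervention arm regarding outcome" and its columns are headed N=203 and N=101. Its onset-day rows carry two tests. One is a Mann-Whitney test (statistic 2.391, p=0.017) on means of 3 and 4.13 days and medians of 2 and 4. The other is a chi-square on the day-by-day counts (10.150, p=0.118).

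The text beneath the table begins with arm denominators: "15 contacts (7.4%) developed COVID-19 in the ivermectin arm compared to 59 (58.4%) in the no-intervention arm". It then reports timing: "The median (range) days for developing the disease was 2 (2-6) in ivermectin group compared and 4 (2-10) in the no-intervention group", and calls that difference significant, printing p<0.017 where the table has p=0.017. Next come "Ten contacts (66.6%) developed symptoms in" the first 3 days on ivermectin, and "In the no-intervention arm, 25 (42.3%) developed symptoms in the" same period.

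No row label, footnote or sentence says that the onset figures are restricted to ill contacts. For HRCT and blood count, by contrast, the text does give the reduced denominators (14 and 58). The Statistical analysis section names the Mann-Whitney test for two groups of non-normal data. It mentions no such restriction and plans no time-to-event or cumulative-incidence method. The Follow up section sets the horizon: "These asymptomatic persons will be followed up for 2 weeks after the diagnosis of index case".

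**The concern.** An onset day exists only for someone who fell ill, and falling ill is what the trial set out to prevent. When 7.4% of one arm and 58.4% of the other supply the data, the two sets of onset days come from groups selected on the outcome at very different rates. A rank test between them does not compare the arms, whatever its p-value.

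The reader of Table (2) sees two significant results under the same arm headings: less illness, and a shorter time to illness. Only the first is a comparison of the arms. The unannounced move in the text from arm denominators to shares of the ill makes this easy to miss. At stake is the reading of a secondary timing result, not the main finding.

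**Working it through.** **Inputs, all from Table (2).** Onset on days 2, 3, 4, 5, 6, 7, 10: ivermectin 8, 2, 3, 1, 1, 0, 0 (sum 15); no intervention 12, 13, 11, 13, 1, 8, 1 (sum 59). Arms: 203 and 101.

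**Step 1: reproduce the printed tests.**
- Means: 45/15 = 3.00 and 244/59 = 4.14. Medians: 2 and 4.
- Mann-Whitney U = 8×6 + 2×18.5 + 3×30.5 + 42.5 + 49.5 = 268.5. Expected value 15×59/2 = 442.5.
- Tied-group sizes are 20, 15, 14, 14, 2, 8, 1, so Σ(t³−t) = 17,310. Variance = (15×59/12) × [75 − 17,310/(74×73)] = 73.75 × 71.796 = 5,294.9; SD = 72.77.
- z = (442.5 − 268.5)/72.77 = 2.391, p = 0.0168. Table (2) prints 2.391 and 0.017.
- Chi-square on the 2×7 day table: 10.150 on 6 df, p = 0.118, as printed.

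Both printed tests therefore rest on 74 of the 304 contacts. As a cross-check, a rank test on all 304, with symptom-free contacts set to day 14, gives z = 9.31 in the other direction, so p=0.017 cannot come from the full arms.

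**Step 2: identify the denominators in the text.**
- 66.6% is 10/15 and 42.3% is 25/59: the share of illnesses that began by day 3.
- Over the arms, 10/203 = 4.9% and 25/101 = 24.8%: the risk of being ill by day 3.

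**Step 3: cumulative illness over all contacts** (running count divided by 203 or 101, no losses assumed).

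| By day | Ivermectin | No intervention | Difference (points) |
|---|---|---|---|
| 2 | 8 (3.9%) | 12 (11.9%) | 7.9 |
| 3 | 10 (4.9%) | 25 (24.8%) | 19.8 |
| 4 | 13 (6.4%) | 36 (35.6%) | 29.2 |
| 5 | 14 (6.9%) | 49 (48.5%) | 41.6 |
| 6 | 15 (7.4%) | 50 (49.5%) | 42.1 |
| 7 | 15 (7.4%) | 58 (57.4%) | 50.0 |
| 10 | 15 (7.4%) | 59 (58.4%) | 51.0 |

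The ivermectin arm is lower at every listed day. The shorter median onset on ivermectin appears only among those who became ill.

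**Step 4: other rows with the same restriction.** The CT rows sum to 7+7 = 14 and 30+28 = 58. The CBC rows sum to 2+12 = 14 and 5+53 = 58. They too are tested among ill contacts under the N=203 and N=101 headings, although the text states their denominators.

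**The case against.** The strongest reply is that this is a missing label and little more. Days to symptoms can be defined only in people with symptoms, the day counts sum to 15 and 59 just below the row giving those totals, and the printed percentages (8 as 53.3%, 12 as 20.3%) show the base. This stands in part: a careful reader can infer the restriction. But the mean, median and p=0.017 rows carry no label, and the text reports significance between the groups with no caveat.

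A second reply is that the conditional figures are legitimate description. This stands in full. A reader might take 4.9% v 24.8% as showing that 66.6% v 42.3% is wrong. It is not. One pair is the share of illnesses that began early and the other is the risk of early illness, and both are true at once.

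A reader might also infer that the documents claim that ivermectin brings symptoms on sooner. They do not; the text reports the medians and the p-value without that interpretation. Nor do the figures establish such an effect, since the two groups of ill contacts were selected by the outcome.

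Finally, the day counts might suggest that the relative effect changes over time. The strength of any such contrast depends on where the days are cut after seeing the data, so it is not part of this point.

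**Conclusion.** The point holds as a minor correction to a secondary result. The two p-values are calculated correctly for the 74 ill contacts, but they do not compare the arms, and the text presents p=0.017 as though it did. The all-contact comparison that can be built from the same counts runs from 3.9% v 11.9% at day 2 to 7.4% v 58.4% at day 10.

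A reader might conclude that the main finding is affected. It is not: 15/203 v 59/101 already uses every contact. Equally, the cumulative figures do not settle how the arms were formed or whether they are comparable.

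Those figures assume that all 304 contacts were followed for the planned 2 weeks; losses cannot be read from the text available here. No intervals are attached, because contacts share index cases and the documents give neither household sizes by arm nor an intracluster correlation. Removing the p-values depends on none of this.

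**What to change.** - Remove p=0.017 and p=0.118 from Table (2), and the significance statement from the text.
- Keep the onset days and the 66.6% and 42.3% figures as description, labelled *among contacts who became ill (n=15, n=59)*.
- Label the CT and CBC rows in the same way (n=14, n=58).
- Add cumulative illness over all 304 contacts: at least day 2, 3.9% v 11.9%; day 3, 4.9% v 24.8%; day 5, 6.9% v 48.5%; day 10, 7.4% v 58.4%. State time zero and any losses.
- Where individual follow-up and household identifiers are available, show this as a curve censored at 2 weeks, with household-clustered intervals.

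The deletions, labels and cumulative columns need only counts already printed, so they cost almost nothing. The curve and the clustered intervals need the individual records and household identifiers, and a short additional analysis.
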